7.2.6 Adverse Event Reporting

Adverse events (AE) will be monitored at every study visit after Visit 1. This will be done by asking participants if they have experienced any new or worsening symptoms. If the participant indicates a new or worsening symptom, an adverse event form will be completed. This form will document the date of AE report, the start and end date of the symptom, a description of the AE, the outcome, the severity, and the action taken to resolve the symptom. Finally, it will be determined by the medical monitor if the symptom is related to the study.

7.2.7 Appointment Reminders

Phone call reminders will be used throughout the study to remind participants of their visit (approximately two days prior). Also, screening visit confirmation and directions will be

emailed/mailed to the participant prior to Visit 1. (SEE ATTACHMENT: First Appointment Reminder and Appointment Phone Call Text).

7.2.8 Daily Dairies for ECIG and Cigarette Use

Prior to randomization, participants will be asked to track the number of cigarettes smoked per day using a paper daily diary. They will also receive a daily REDCap survey link via text message (through Twilio) to enter their cigarette usage. During the 4-week ECIG conditioning period, participants will be required to record their ECIG use (in puffs per day) and the number of cigarettes smoked. A paper-based daily diary designed for data collection of each product type will be used. Participants will also continue reporting their use via REDCap survey links each evening. Research assistants will review the data entered by participants via the REDCap survey links at each visit. If participants did not complete the survey online, the researcher will ask the participant at each visit their ECIG and cigarette use. The diary will be used as a memory aid for the participant. (SEE ATTACHMENT: Cigarette Pack Daily Diary and E-cigarette and Cig Daily Diary)

7.2.9 MRI Scan Details

The 45-minute MRI scan will begin with a 10-minute T1-weighted high resolution anatomical scan and a 5-minute resting state scan, followed by the odor cue-reactivity functional task. Scans will be conducted on a Siemens 3T Prisma-Fit scanner (Siemens Healthineers, Erlangen, Germany) equipped with a 64-Channel head coil. Functional images will be collected through T2*-weighted interleaved ascending multiband EPI acquisition in 2.85 x 2.85 x 4mm resolution and slice thickness (TR=600ms, TE=30 ms) with a field of view of 230mm, 80x80 matrix size, and 50° flip angle.

7.2.10 Flavor-Cue Reactivity Details

The olfactometer (ETT, inc: <http://www.emergingtechtrans.com>) will be used to deliver the e-liquid odors to the nose during a respiration-triggered event-related fMRI cue-reactivity task. The tobacco and strawberry vanilla e-liquid flavors, as well as two common control scents, Lavender and PEA (phenyl ethyl alcohol; that smells like rose), will be delivered in randomized order during 4-minute blocks over 8 runs. The flavors will be delivered for 4 seconds every 20-30 seconds depending on respiration rate. At the end of the task, participants will be delivered each odor again and asked to rate how much they like the flavor using a fiber-optic button box.

The lavender odor is an experimental control condition that encourages participants to maintain attention and task engagement during the MRI scan. It provides us with a quality control manipulation, whereby if we suspect from poor data quality that a participant was not paying attention in the scanner, we can confirm this if they were also not responding to the lavender scent as instructed.

7.3 Duration of Participation

All participants will be in the study for a period of at least 5 weeks but no more than 8 weeks and will attend 2 in-person clinic visits at the study center. The randomization/pre-conditioning visit (Visit 2), remote check in (Visit 3) and post-conditioning visit (Visit 4), will happen within a 4 week period.

7.4 Test Article(s) (Study Drug(s) and/or Study Device(s))

7.4.1 Description

The ECIG used will be the EGO ECIG. Previous work has shown that the EGO ECIG was capable of delivering nicotine to its users.²⁶ This ECIG is made up of 2 parts, a battery and a cartomizer. The cartomizer contains the heating element and the liquid. The liquid used in the cartomizer will contain either 0 mg/ml or 18 mg/ml of nicotine and be either tobacco or strawberry vanilla

flavor. The nicotine concentration in the liquid and the flavor will be determined by random assignment. The cartomizers will be filled with liquid by the researchers and will be used once by the participant and returned to researchers.

7.4.2 Treatment Regimen

Participants will be randomized to one of four conditions:

- Tobacco flavor ECIG (18 mg/ml nicotine concentration)
- Tobacco flavor ECIG (0mg/ml nicotine concentration)
- Strawberry Vanilla flavor ECIG (18 mg/ml nicotine concentration)
- Strawberry Vanilla flavor ECIG (0mg/ml nicotine concentration)

Participants will be instructed to use their ECIG for at least 50 puffs per day to replace conventional cigarette use.

7.4.3 Method for Assigning Subject to Treatment Groups

Blocked randomization stratified across gender and matched for age will be accomplished with a 1:1:1:1 ratio of condition assignments with a goal of 56 randomized over a 7 month recruitment period. The randomization list will be stored in a password protected document that will only be accessed by unblinded study personnel.

7.4.4 Subject Compliance Monitoring

The importance of honest reporting will be stressed to participants. Compliance to the instructions for ECIG use will be determined by the daily diary procedure and the amount of product used. Unused products will be collected, weighed, and recorded. We emphasize that compliance issues should be minimal given the fact that participants remain in the study while continuing to use conventional tobacco cigarettes.

7.4.5 Blinding of the Test Article

The study ECIGs will be received by unblinded study staff. Unblinded staff will appropriately package the cartomizers and ECIG parts into packs/kits for the participants. The kits will be assigned numbers and the participants will be randomly assigned the kit number at the randomization visit (Visit 2). The blinded research assistant will not be involved in the packing and labelling of the kits. The blinded research assistant will be told what participant is assigned to which kit, which will maintain the blind.

7.4.6 Receiving, Storage, Dispensing and Return

7.4.6.1 Receipt of Test Article

The ECIG will be purchased online in its standard packaging and shipped to Penn State. Empty cartomizers also will be purchased online. The ECIG liquid will be purchased from reputable online ECIG liquid vendors.

7.4.6.2 Storage

All study products (ECIG batteries, cartomizers, liquid) and components will be stored in a locked closet away from light, heat, and moisture.

7.4.6.3 Preparation and Dispensing

The unblinded study staff will be responsible for filling the cartomizers with the appropriate nicotine concentration (0mg/ml or 18 mg/ml) and flavor (tobacco or strawberry vanilla) in a biological safety cabinet. Filled cartomizers will be stored in bottles/bags with child-proof caps. Once filled, unblinded staff will then put cartomizer-containing bottle into ECIG kits

labelled with unique identifiers in order to track bottles and maintain blinding. Unblinded staff will appropriately package kits for the participants. At the randomization visit (Visit 2), participants will be randomly assigned a Randomization ID that matches a kit number. The blinded research assistants will not be involved in the packing and labelling of the kits. The blinded research assistant will be told what participant is assigned to which Randomization ID, which will maintain the blind.

7.4.6.4

Return or Destruction of the Test Article

Participants will be permitted to keep their ECIG device at the end of the study. Participants will be required to return all used and unused cartomizers to the research assistant at each clinic visit using provided containers/bags. Participants will not keep unused cartomizers at the end of the study. If a participant is withdrawn for medical reasons (CVD event), they will be asked to return their device/cartomizers via a pre-paid envelope to the study center.

7.4.6.5

Prior and Concomitant Therapy

Concomitant medications will be collected regularly throughout the trial to serve as covariates during analysis and to monitor participant health conditions. Medications related to certain medical conditions that are exclusions to the study, such as COPD and current heart conditions, will serve to alert the study staff of the presence of these conditions during screening.

8.0 Subject Numbers and Statistical Plan

8.1 Number of Subjects

Up to 75 subjects may be enrolled in this study in order to have 56 randomized subjects. We will continue to consent participants to the study until we reach 56 randomized subjects.

8.2 Sample size determination

For the proposed between-subject analyses, we will be looking for trends in the hypothesized direction, not statistical significance with traditional parametric statistics. With an estimated medium effect size, we will have approximately 50% power to find a liberal between-subject effect ($p<.10$) for the proposed t-test between the flavor groups on baseline cue-reactivity, 60% power to detect changes in cue-reactivity between the nicotine content and flavor groups, and 90% power to detect within-subject changes in cue-reactivity at $p<.05$. Groups will be stratified by gender to estimate gender effects for future research.

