1.0 Objectives

1.1 Study Objectives

The current proposal aims to establish proof-of-concept that neural cue-reactivity can serve as an early, objective marker of electronic cigarette (ECIG) addictive potential. Further, this proposal will examine the effect of flavor and nicotine concentration on the addictive potential of ECIGs to aid research informing U.S. Food and Drug Administration (FDA) flavor regulations and smoking cessation.

The specific aims of the study are:

Aim 1: Determine if smokers and e-cigarette users have pre-conditioned neural cue-reactivity to tobacco or fruit-flavored ECIG odors.

Aim 2: Examine the effect of flavor and nicotine on ECIG odor cue-reactivity after conditioning.

Aim 3: Determine if strawberry vanilla flavor results in stronger cue-reactivity than tobacco flavor.

Hypothesis: We expect the group assigned to the 18 mg/ml strawberry vanilla flavor to show larger increases in neural cue-reactivity to their assigned odor than the 18 mg/ml tobacco flavor group.

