Aim 2: Examine the effect of flavor and nicotine on ECIG odor cue-reactivity after conditioning. Two-sample t-test will be conducted in FSL for the strawberry vanilla>rose and tobacco>rose odor difference score z- statistic images comparing the 18 mg to 0mg nicotine content ECIG groups. A paired two-sample t-test will be conducted to compare the tobacco>rose and strawberry vanilla>rose odor difference score z-statistic image separately for each 18 mg/ml ECIG flavor group. These t-tests will identify anatomical regions with significant effects of nicotine level and assigned vs. unassigned flavor over time. We expect that BOLD activity in regions implicated in smoking cue-reactivity will increase more over the conditioning phase for the 18 mg nicotine group compared to the 0mg nicotine group and for odors from the assigned vs. unassigned flavor.

Aim 3: Determine if strawberry vanilla results in stronger cue-reactivity than tobacco flavor. A two-sample t-test will be conducted for the assigned flavor (strawberry vanilla or tobacco) > control rose difference score z- statistic images comparing the flavor groups. These t-tests will identify anatomical regions with significant flavor group (tobacco vs. strawberry vanilla) by time (baseline to post-randomization) interaction effects on each odor image. For this analysis, only the 18 mg/ml nicotine content flavor groups will be included.

Exploratory Behavioral Aim: Determine if changes in flavor cue-reactivity are associated with changes in ECIG satisfaction, liking, craving, and dependence. One-sample t-tests will assess for anatomical regions where BOLD changes in odor cue-reactivity are correlated with changes in behavioral measures of e- cig satisfaction, craving, and dependence collected at the 2-week check-in and post-randomization visit, and changes in ECIG liking collected at the baseline and post-randomization visits.

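### Section 8.2 sets significance aside for the between-subject comparisons in favor of an undefined trend, and this is not reconciled with its own p<.10 power or with the significant regions of section 8.3

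*Combined protocol and SAP*

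**What the plan says.** Section 8.2 states that, for the between-subject analyses, "we will be looking for trends in the hypothesized direction, not statistical significance with traditional parametric statistics". No cut-off, interval, region or summary measure is attached to the word trend.

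The next sentence of 8.2 opens "With an estimated medium effect size" and gives "approximately 50% power to find a liberal between-subject effect ($p<.10$) for the proposed t-test between the flavor groups on baseline cue-reactivity", then "60% power to detect changes in cue-reactivity between the nicotine content and flavor groups". The p<.10 is tied explicitly only to the first of these. The 60% figure has no alpha of its own, and sidedness is not stated for either.

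Section 8.3 plans two-sample t-tests for the nicotine comparison (Aim 2) and the flavor comparison among the 18 mg/ml arms (Aim 3). Of the Aim 2 tests it says: "These t-tests will identify anatomical regions with significant effects of nicotine level and assigned vs. unassigned flavor over time". Aim 3 is worded in the same way. Neither has an alpha or a multiple-comparison threshold.

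Section 1.1 says the proposal "aims to establish proof-of-concept that neural cue-reactivity can serve as an early, objective marker" of e-cigarette addictive potential.

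**The concern.** The randomized comparisons of nicotine level and flavor carry the proof-of-concept claim. For these, 8.2 sets error control aside and leaves direction as the only stated content of the criterion. A rule whose only input is the sign of an estimate cannot distinguish a real effect from none. The power figures that follow belong to a different rule, and 8.3 implies yet another.

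An analyst could therefore report a non-significant difference in the predicted direction as support, cite 8.2, and be within the plan. Another analyst could call the same result negative under 8.3. The plan does not settle which is right.

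**Working it through.** **Inputs**

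- Total randomized: 56 (section 8.1: "Up to 75 subjects may be enrolled in this study in order to have 56 randomized subjects"). Loss to follow-up is not stated and is taken as zero.
- Allocation 1:1:1:1 (section 7.4.3), so 56/4 = 14 per arm.
- Aim 2 nicotine comparison, read as pooling the two flavors: 28 vs 28. Aim 3 uses only the 18 mg/ml arms (section 8.3): 14 vs 14.
- Effect size: the plan says medium and gives no number. d = 0.5 is assumed, in standard deviations of the quantity compared.
- One pre-chosen region and one contrast, with no voxelwise correction.

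**Step 1: the plan's own figures.** For n per group, the standardized shift is δ = d√(n/2).

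- n = 14: δ = 0.5 × √7 = 1.323.
- n = 28: δ = 0.5 × √14 = 1.871.

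The normal approximation to power in the predicted direction is Φ(δ − z). The noncentral t gives the values in the last column.

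| Comparison | Level | Normal approximation | Noncentral t |
|---|---|---|---|
| 14 vs 14 | one-sided .10 | Φ(1.323 − 1.282) = 0.516 | 0.508 |
| 28 vs 28 | two-sided .10 (one-sided .05) | Φ(1.871 − 1.645) = 0.589 | 0.580 |
| 14 vs 14 | two-sided .10 (one-sided .05) | Φ(1.323 − 1.645) = 0.374 | 0.361 |
| 28 vs 28 | one-sided .10 | – | 0.717 |

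The stated 50% reproduces as 14 vs 14, one-sided .10. The stated 60% reproduces as 28 vs 28, two-sided .10. Both are thus the power of threshold tests. At d = 0.5 and p<.10 they need different group sizes and different sidedness, so even the p<.10 reading is not a single rule.

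**Step 2: the literal, direction-only reading.** The probability that the estimate has the predicted sign is Φ(δ).

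- No effect: Φ(0) = 0.50, at any sample size.
- d = 0.5, 14 vs 14: Φ(1.323) = 0.907.
- d = 0.5, 28 vs 28: Φ(1.871) = 0.969.

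Neither 0.907 nor 0.969 is near the stated 50% or 60%.

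**Step 3: the p<.10 reading.** Under no effect the rate is 10% per test. If the test is two-sided, 5% falls in the predicted direction. At d = 0.5 the two-sided test is met in the predicted direction with probability 0.361 (14 vs 14) or 0.580 (28 vs 28).

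**Step 4: how informative a positive result is** (probability at d = 0.5 divided by probability under no effect).

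| Rule | 14 vs 14 | 28 vs 28 |
|---|---|---|
| Direction only | 0.907/0.50 = 1.8 | 0.969/0.50 = 1.9 |
| Two-sided p<.10, predicted direction | 0.361/0.05 = 7.2 | 0.580/0.05 = 11.6 |

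**The case against.** The strongest reply is that the protocol never defines a sign rule. The sentence on trends and the sentence with p<.10 are adjacent, and a natural reading is that the trial will use .10 in place of the traditional level and call that a trend. The rate under no effect is then 10%, not 50%. Section 8.3 supports this. It specifies two-sample t-tests on statistic images, and a bare sign rule could not pick out regions there, because under no effect about half of all voxels would have the predicted sign.

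Much of this stands. A reader might infer that the plan adopts a rule with a 50% false-positive rate. The documents do not support that as fact; it is the consequence of one literal reading. A reader might also infer still higher rates from counting several regions or both Aim 2 nicotine contrasts. That is not supported either. The four named regions in 8.3 belong to the Aim 1 baseline contrasts, nothing says that one region of several would suffice, and the correlation between contrasts is not given.

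The p<.10 reading nevertheless does not close the gap. The protocol does not equate a trend with p<.10. It ties that level only to a baseline flavor-group t-test, which does not appear in 8.3, where Aim 1 uses one-sample tests. The alpha for the comparisons of change is unclear, and a t-test at p<.10 is itself the kind of parametric significance test the preceding sentence sets aside.

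It is also fair to say that the plan is an open proof-of-concept study with candidly low power. That justifies wide intervals and inconclusive results. It does not justify leaving out the threshold for claiming support.

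**Conclusion.** The concern holds as a conflict between three unreconciled criteria: direction only, p<.10, and significant regions with no alpha. Depending on the reading, the chance that one pre-chosen region and contrast counts as support under no effect is 50%, 10%, or 5% (two-sided .10, predicted direction). The plan does not say which applies to Aims 2 and 3.

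The 50% needs no assumption about effect size or sample size beyond an estimate symmetric about zero under no effect. The 91%, 97%, 36% and 58% rest on d = 0.5, no dropout and a single test. The point should be settled before analysis. It does not undermine the randomization or the data to be collected.

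**What to change.** Replace the sentence on trends in section 8.2 with one rule, for example:

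> For the between-subject tests of Aims 2 and 3, we will report the estimated group difference in change in [pre-specified regional summary] with its 90% confidence interval. The level for these tests is two-sided p<.10. Support will be stated only when the interval excludes zero in the predicted direction. A difference in the predicted direction whose interval includes zero will be reported as inconclusive.

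Two further additions are needed.

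- In 8.3, state a separate corrected threshold for any voxelwise regions called significant. The rule above should not turn that word into uncorrected p<.10.
- In 8.2, state the power under this rule at d = 0.5: about 58% for 28 vs 28 (Aim 2 nicotine) and 36% for 14 vs 14 (Aim 3). The .10 level has to be declared for these tests, because 8.2 does not clearly state power at that level for them.

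The cost is a short wording change and no new data, but a region and summary measure must be named and extracted, which 8.3 does not now provide. Fewer results can be called supportive: at d = 0.5, 58% and 36% rather than the 97% and 91% that direction alone would allow.

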8.3 Statistical methods

Images collected during the fMRI odor cue reactivity task will be preprocessed using a standard Functional Magnetic Resonance Imaging of the Brain Software Library (FSL) software pipeline. Blood oxygen level dependent (BOLD) activation during the tobacco, strawberry vanilla, and rose flavors will be modeled using a double-gamma hemodynamic response function, contrasted to one another, and merged across the two runs for each participant. To create images that capture changes from baseline to post-conditioning, a difference z- statistic image will be calculated by subtracting the baseline image from the post-conditioning image. The lavender odor is an experimental control condition that encourages participants to maintain attention and task engagement during the MRI scan. It is not part of the endpoints of the study.

Aim 1: Determine if smokers and ECIG users have pre-conditioned neural cue-reactivity to tobacco or strawberry-vanilla ECIG odors. One- sample t-test will be conducted on the contrast of tobacco > strawberry vanilla, tobacco > rose, strawberry vanilla > rose to identify anatomical brain regions where tobacco elicits greater neural activation over strawberry vanilla and rose odors and strawberry vanilla elicits greater activation over rose odors. We expect tobacco odor to elicit greater activation in the ventral striatum, amygdala, anterior insula, and OFC than the strawberry vanilla and rose for combustible cigarette smokers and tobacco-flavored e-cigarette users. We expect strawberry-vanilla odor to elicit greater activation in ventral striatum, amygdala, anterior insula, and OFC than tobacco and rose for fruit-flavored e-cigarette users.

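### The 90% and 60% power figures in Section 8.2 are not tied to named tests, and the n = 14 tests in Section 8.3 do not reach them if the medium effect is 0.5

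*Combined protocol and SAP*

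**What the plan says.** Section 8.2 bases three power figures on one medium effect size, to which it gives no number.

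- About 50%, at p<.10, for "the proposed t-test between the flavor groups on baseline cue-reactivity".
- One 60% for change between groups and a 90% for change within subjects: "60% power to detect changes in cue-reactivity between the nicotine content and flavor groups, and 90% power to detect within-subject changes in cue-reactivity". The 90% is at p<.05. It is not clear whether the 60% uses .10 or .05.
- For the between-subject analyses the section says "we will be looking for trends in the hypothesized direction" rather than conventional significance.

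Section 7.4.3 sets a goal of 56 randomized at 1:1:1:1. Section 3.3.2 provides replacement only for withdrawals before randomization.

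Section 8.3 lists these tests:

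- Aim 1: a one-sample "t-test will be conducted on the contrast of tobacco > strawberry vanilla" and on two further baseline odor contrasts.
- Aim 2, nicotine: a two-sample test on change images, "comparing the 18 mg to 0mg nicotine content ECIG groups".
- Aim 2, odor: a paired test of the change for one odor against the change for the other, run "separately for each 18 mg/ml ECIG flavor group".
- Aim 3: a two-sample test of change between flavor groups, in which "only the 18 mg/ml nicotine content flavor groups will be included".
- Exploratory: one-sample tests for regions where "BOLD changes in odor cue-reactivity are correlated with changes in behavioral measures".

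**The concern.** The power figures cannot be matched to the listed tests. The 90% is the only high-power statement in Section 8.2 and carries an explicit p<.05. A reader will attach it to the only within-subject change comparisons in Section 8.3, the Aim 2 paired tests, which have 14 participants each. A null result there could then be taken as informative when it is not. The single 60% covers two comparisons, one with twice as many participants per group as the other. The smaller one, Aim 3, carries the only hypothesis stated in Section 1.1. The 50% is for a two-group baseline test that Section 8.3 does not contain.

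**Working it through.** **Inputs.** 56 / 4 = 14 per arm (Section 7.4.3). From Section 8.3: nicotine test 28 vs 28, Aim 3 test 14 vs 14, Aim 2 paired tests n = 14 each. Alpha is .05 for the 90%; .10 is used for the between-group tests, which favors the plan. The effect is assumed to be 0.5, standardised on the image each test analyses. Sidedness is not stated, so both versions are given.

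**Method.** Power from the noncentral t distribution. Paired or one-sample: noncentrality dz × √n, df = n − 1. Two-sample with n per group: noncentrality d × √(n/2), df = 2n − 2.

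**1. Trying to reproduce the 90% (alpha .05, dz = 0.5)**

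| n | Noncentrality | Two-sided | One-sided |
|---|---|---|---|
| 14 (Aim 2 paired test, as listed) | 0.5 × √14 = 1.87 | 41.0% | 55.1% |
| 28 (both 18 mg/ml groups together) | 0.5 × √28 = 2.65 | 72.3% | 82.5% |
| 44 (pooled pre/post, not listed) | 0.5 × √44 = 3.32 | 90.0% | 94.7% |
| 56 (pooled pre/post, not listed) | 0.5 × √56 = 3.74 | 95.7% | 98.0% |

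Reaching 90% with n = 14 needs dz of 0.94 two-sided or 0.83 one-sided. If 0.5 is instead in raw SD units, dz = 0.5 / √(2(1 − r)), where r is the correlation between the two odor change scores. Then 90% needs r = 1 − (0.5/0.938)²/2 = 0.86 two-sided, or 1 − (0.5/0.827)²/2 = 0.82 one-sided. No correlation is stated.

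**2. Trying to reproduce the 60% (d = 0.5)**

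| Test | Noncentrality | .10 two-sided | .10 one-sided | .05 two-sided | .05 one-sided |
|---|---|---|---|---|---|
| Nicotine, 28 vs 28 | 0.5 × √14 = 1.87 | 58.0% | 71.7% | 45.1% | 58.0% |
| Aim 3, 14 vs 14 | 0.5 × √7 = 1.32 | 36.2% | 50.8% | 24.7% | 36.1% |

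The 60% is approximately right for the nicotine test at two-sided .10 or one-sided .05. It fits Aim 3 under none of the four settings.

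**3. Can one 60% hold for both tests at any effect size?** Solve for the d that gives one test 60%, then apply that d to the other.

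| Alpha, sides | d for 60% at 28 vs 28 | Power, 14 vs 14 | d for 60% at 14 vs 14 | Power, 28 vs 28 |
|---|---|---|---|---|
| .10, two | 0.514 | 37.5% | 0.737 | 85.9% |
| .10, one | 0.413 | 41.9% | 0.590 | 81.8% |
| .05, two | 0.602 | 33.6% | 0.869 | 89.1% |
| .05, one | 0.514 | 37.4% | 0.737 | 85.9% |

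It cannot. This result does not depend on what medium means.

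**4. The 50%.** A 14 vs 14 test at one-sided .10 gives 50.8%, so a baseline comparison of the two 18 mg/ml arms is one possible source. Section 8.3 lists only one-sample baseline tests, and Section 8.2 does not name the groups.

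**5. Direction of what is left out.** Fourteen per arm is a maximum, because withdrawals after randomization are not replaced. All figures are for a single test, whereas Section 8.3 searches for regions across the brain.

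**The case against.** The strongest reply has four parts.

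- **The 90% may belong to another test.** Section 8.2 speaks of within-subject changes and does not mention the Aim 2 paired tests. A pooled baseline-to-post test reaches 90.0% at n = 44. This reading is plausible, but Section 8.3 lists no such test. The exploratory one-sample tests use BOLD change but assess its correlation with behavior. So either the figure is wrong for the listed tests or its test is missing.
- **The flavor groups behind the 60% may be the 28 vs 28 margin.** Then about 58% would fit both factors at two-sided .10. But the only between-flavor-group test of change in Section 8.3 is restricted to the 18 mg/ml arms, so the figure would describe an unlisted test.
- **Medium may mean 0.5 in raw SD units.** With a baseline-to-post correlation of 0.8, d on the change score is 0.5/√0.4 = 0.79, and Aim 3 at .10 has 65% two-sided or 78% one-sided. So the Aim 3 shortfall does depend on the reading. The same value puts the nicotine test at 90% to 95%, so a common 60% still fails. A correlation of 0.8 between the odor change scores leaves the paired test at 78% to 88%, still under 90%.
- **The plan is open about low between-group power.** It calls these analyses a search for trends at a liberal alpha. That stands, and it reduces the weight of the 60%. It does not cover the within-subject 90%.

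**Conclusion.** The concern holds. Two parts need no assumption about the effect size: a single 60% cannot apply to both a 28 vs 28 and a 14 vs 14 test at a common effect, alpha and sidedness, and the 50% is for a two-group baseline test absent from Section 8.3. The rest assumes that medium is a standardised 0.5 on the analysed image. On that basis the Aim 2 paired tests fall 35 points (one-sided) to 49 points (two-sided) below 90%, and Aim 3 at .10 falls 9 points (one-sided) to 24 points (two-sided) below 60%. The 90% is attainable in this sample only for a pooled test that the plan does not list. The matter should be fixed. The 90% is the more important figure, because the trend wording already tempers the 60%.

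**What to change.** Rewrite Section 8.2 test by test. For each figure, name the test in Section 8.3 and give its n, numeric effect size, alpha and sidedness. If medium is a standardised 0.5:

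- Aim 2 paired tests (n = 14 in each flavor group, alpha .05): replace 90% with 41% two-sided or 55% one-sided.
- Aim 3 (14 vs 14, alpha .10): replace 60% with 36% two-sided or 51% one-sided.
- Aim 2 nicotine test (28 vs 28, alpha .10): state 58% two-sided or 72% one-sided.

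If another effect size or scale was meant, state it, with any correlation it relies on, and recompute. If the 90% was meant for a pooled baseline-to-post test, add that test and its n to Section 8.3 and still report the n = 14 power of the paired tests. Name the groups and test behind the 50%, or remove the figure. Add that 14 per arm is a maximum and that these are single-test powers that do not cover a voxelwise search.

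The cost is wording in Section 8.2, plus a line in Section 8.3 only if a pooled pre/post test or a two-group baseline test is intended. No extra participants are needed, and the Aim 2 and Aim 3 tests do not change. The only downside is less favorable stated power.
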